2.0. Objectives of the Study

2.1. Efficacy

The primary aim of this multicenter, international, randomized, open-label, phase 3 trial is to determine the efficacy of intra-clot catheter placement and aspiration of hematoma contents, followed by gentle clot irrigation with low dose recombinant tissue plasminogen activator (rt-PA), referred to as Minimally Invasive Surgery plus rt-PA (MIS+rt-PA). The primary hypothesis of this trial is that the MIS+rt-PA approach to intracerebral hemorrhage (ICH) management will result in more patients having overall better functional outcome at 365 days, as defined by the proportion of subjects with dichotomized, adjudicated modified Rankin Scale (mRS) score 0-3 vs. 4-6, when compared to the mRS scores for patients managed with standard aggressive medical treatment. Although the mRS includes a category for death, and hence the primary analysis incorporates mortality outcomes, in-hospital and 30-day mortality will also be examined as safety outcomes for the trial. Furthermore, 365-day mortality will be evaluated separately as a secondary efficacy outcome. An intent-to-treat (ITT) paradigm for the analyses will be incorporated. The MISTIE III trial will enroll a total of 500 eligible patients, 250 randomized each treatment arm (MIS+rt-PA or medical management). The power to detect (88%) is for an estimated effect size of 13% across all clot locations with this sample size (500).

Additional analyses of efficacy outcomes will evaluate the therapeutic benefit of MIS+rt-PA relevant to medical management in improving subjects' function and quality of life at 365 days post symptom onset as measured by extended Glasgow Outcome Scale (eGOS), days in various locations such as home

Minimally Invasive Surgery Plus rt-PA for ICH Evacuation Phase 3

during the 365-day period, patient disposition at 180 and 365 days including proportion of days in longterm care facilities, National Institutes of Health Stroke Scale (NIHSS), Barthel score, days in hospital, days in intensive care unit (ICU), Stroke Impact Scale (SIS), Preference-Based Stroke Index (PBSI), EuroQol-5 Dimension (EQ-5D), Mini-Mental State Examination (MMSE), Personal Health Utility Interview, and Center for Epidemiological Studies – Depression (CES-D).

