2.3. Safety

The safety of MIS+rt-PA relative to medical management is assessed by comparing the proportion of subjects between the two groups with treatment-related SAEs within the 30-day time frame: mortality, rebleeding, infection, and first-week (designated as operative mortality for the surgical group) mortality. Additionally, the number and proportion of all SAEs across the entire time frame in the respective randomized groups will be evaluated starting with the follow-up time frames of 180 and 365.

Interim safety analyses will be prepared for the external Data Safety and Monitoring Board (DSMB) on a pre-arranged schedule (such as semi-annual or after enrollment of a fixed number of subjects) to evaluate efficacy and safety. Safety measures include: monitoring the incidence of symptomatic and asymptomatic intracranial bleeding events (i.e., hemorrhage extension, new hemorrhage, catheter-tract hemorrhage) through daily computed tomography (CT) scans for the first four days after randomization and then repeated one day (approximately 24 hours) after ICH catheter removal, and monitoring the incidence of confirmed and suspected infection and in-hospital mortality.

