5.3. Safety Analysis Sample

All randomized subjects are included in the safety analysis sample. Further safety analyses may be determined by clinical events and subgroups of the surgical task.

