6.0. Randomization

Randomization will occur after completed screening for vascular malformation and central validation of inclusion and exclusion criteria. Subjects will be randomized to MIS+rt-PA or medical management using a covariate-adaptive design similar to that used for the CLEAR III trial.² The goal of this randomization scheme is to obtain an improved balance across study arms in the number of subjects with certain prerandomization variables that are most strongly predictive of the functional outcomes (mRS) at 180 and 365 days post-stroke. These variables include pre-randomization clot volume, age, and baseline severity of impairment as measured by GCS. Under this scenario, a randomization scheme will be used which increases a newly enrolled subject's probability of being assigned to the study arm that improves the overall balance in these important prognostic factors. Briefly, prior to randomization for each incoming patient, the imbalance between treatment arms will be determined using the accumulating available data on clot volume, age and GCS. The patient will then be randomized with high probability (e.g., "weighted coin toss") to the treatment arm that lowers the imbalance. Patients at any given site will not be considered for covariate-adaptive randomization until the site has enrolled four or six (blinded; sites are randomized to four or six to maintain blinding) patients into each treatment arm by within-site block randomization. This randomization scheme will be implemented using software included in the MISTIE III EDC (electronic data capture) system similar to what has been successfully implemented in the CLEAR III trial.

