11.0. Efficacy Analyses

11.1. Primary Efficacy Analysis: Dichotomized, Adjudicated mRS 0-3 vs. 4-6 at 365 Days Post Ictus

This primary analysis will produce an estimate and 95% confidence interval for the average treatment effect comparing assignment to MIS+rt-PA treatment (MISTIE) versus control (standard of care, i.e., medical management), using the ITT principle. Specifically, we will estimate the difference between the probability of an adjudicated mRS score of 3 or less at 365 days post-stroke comparing assignment to

treatment versus control; this difference is called the average treatment effect. Below is a description of the procedure for computing estimators of the average treatment effect. We also will test the null hypothesis of zero treatment effect at level 0.05.

To estimate the average treatment effect, we will use the targeted maximum likelihood estimator (TMLE) of van der Laan and Gruber.³ This estimator adjusts for baseline (i.e., pre-randomization) variables in order to improve precision. The baseline variables, denoted by the vector B, include the three variables used in the covariate-adaptive randomization as given in Section 6.0 (i.e., pre-randomization clot volume, age, and baseline severity of impairment as measured by GCS) as well as the following additional variables: IVH volume and location of ICH (indicator of lobar vs. deep). All baseline variables are treated as categorical and included as main terms in the models below.

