Methods of non-inferiority will be used to statistically determine if the proportions of a particular type of SAE, where there are adequate data for a particular type, are not substantially different among both treatment groups in order to test the hypothesis that MIS+rt-PA is as safe as standard medical management. Non-inferiority testing deems the rates of any SAE event in the MIS+rt-PA group to not be substantially greater than the SAE event rate in the standard medical management group as long as the group difference in this rate is statistically within some pre-specified tolerance. For this trial, the tolerance value will be defined as 10% for the primary adverse events of 30-day mortality, rebleeding, and infection, and 5% for first-week operative mortality. Thus, the rates of adverse events seen in the MIS group can be higher than those in the medically managed group, and yet still be considered not substantially different as long as the upper one-sided 95% CIs on rate differences are $\leq 10\%$ or $\leq 5\%$, depending on the safety measure.

Minimally Invasive Surgery Plus rt-PA for ICH Evacuation Phase 3

Since data from the MISTIE phase 2 trial neither supports nor negates any significant difference in SAE event rates by gender, race, or ethnicity, the non-inferiority analyses described above will be performed separately for subpopulations within each of these demographics where there are adequate data available.

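### The 30-day mortality non-inferiority test in SAP 14.1 states no covariate adjustment; standardizing for GCS, age and clot volume would add roughly 1 to 9 points of power at no data cost

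*SAP*

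**What the plan says.** **The test.** Protocol 1.2 makes safety at 30 days a primary objective. SAP 2.3 describes the comparison in simple terms: "The safety of MIS+rt-PA relative to medical management is assessed by comparing the proportion of subjects between the two groups". SAP 14.1 sets the margins: "the tolerance value will be defined as 10% for the primary adverse events of 30-day mortality, rebleeding, and infection", and 5% for first-week operative mortality. Under its criterion, surgical rates may be higher and "still be considered not substantially different as long as the upper one-sided 95% CIs on rate differences are" within the margin. Protocol 9.1.7 (Analyses 1b) has the same criterion under the name of equivalence. Neither text names covariates, an estimator or an interval method. SAP 5.3 gives the analysis set: "All randomized subjects are included in the safety analysis sample".

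**Allocation and efficacy.** On the allocation factors, SAP 6.0 says: "These variables include pre-randomization clot volume, age, and baseline severity of impairment as measured by GCS". (Protocol 9.1.1 lists only clot volume and GCS.) SAP 11.1 uses all three, plus IVH volume and ICH location, in the primary efficacy estimate and gives the reason: "This estimator adjusts for baseline (i.e., pre-randomization) variables in order to improve precision". The instruction to adjust every analysis like the primary one is in the heading of SAP 2.2, which covers efficacy measures only.

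**Adjusted safety models.** SAP 14.2 has a logistic regression for total SAEs, and SAP 14.3 has mixed models that account for confounders. Neither is tied to the 10-point margin.

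**The concern.** The SAP's reason for adjusting the efficacy risk difference applies equally to 30-day death. The factors are baseline variables, already collected and used for allocation, and likely to be prognostic for death. The phase II table in Protocol 2.2 gives, for functional outcome (with death counted as failure), odds ratios of 1.57 to 1.77 per GCS point and 0.91 to 0.96 for age. For clot volume it gives 0.65 per 10 mL univariately, weaker after adjustment.

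What is at stake is the precision of the limit that decides one of the trial's two primary objectives. A second cost comes from the silence itself: if the result falls near 10 points, the choice between a crude and an adjusted limit would be made after the data are seen.

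**Working it through.** **1. Check the formula on the plan's own figure.** The documents state no power for the safety test, so the efficacy figure is used: 25% v 38%, 250 per arm, two-sided 0.05.
- Pooled SE = √(2 × 0.315 × 0.685 / 250) = 0.0415; unpooled SE = √((0.25 × 0.75 + 0.38 × 0.62) / 250) = 0.0411.
- Power = Φ((0.13 − 1.96 × 0.0415) / 0.0411) = 88.1%, against the stated 88%.

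**2. Inputs for the safety test.** SAP 2.1 gives the size: "The MISTIE III trial will enroll a total of 500 eligible patients, 250 randomized each treatment arm". The margin M is 0.10 with one-sided alpha 0.05 (SAP 14.1). Phase II 30-day mortality was 10% medical and 15% surgical (Protocol 2.2).

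**3. Crude power.** With d the true surgical excess, power = Φ((M − d)/SE − 1.645), where SE = √((p₀q₀ + p₁q₁)/250).
- 10% v 15%: SE = √(0.2175/250) = 0.0295; 0.05/0.0295 = 1.695; Φ(0.050) = 52.0%. The one-sided half-width is 1.645 × 2.95 = 4.85 points.
- 15% v 15%: SE = √(0.255/250) = 0.0319; Φ(3.131 − 1.645) = 93.1%.
- 10% v 10%: SE = √(0.18/250) = 0.0268; Φ(3.727 − 1.645) = 98.1%.

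**4. Adjusted power, ideal case.** Multiply SE by √(1 − R²), where R² is the share of mortality variance that the covariates explain. The documents give neither R² nor AUC for mortality, so the range is an assumption. A logistic model with a normal linear predictor at 12.5% mortality converts AUC to R².

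| AUC (R²) | 10% v 15% | 15% v 15% | 10% v 10% |
|---|---|---|---|
| crude | 52.0% | 93.1% | 98.1% |
| 0.75 (0.107) | 55.9% | 95.2% | 98.9% |
| 0.80 (0.166) | 58.4% | 96.3% | 99.3% |
| 0.85 (0.246) | 62.1% | 97.5% | 99.6% |

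These gains are optimistic, because the prognostic score is treated as known.

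**5. With the model estimated.** Simulation with 250 per arm and logistic standardization fitted to the data pays the cost of estimation.
- Three continuous covariates, simple 1:1 allocation, 2,000 trials per setting: at 10% v 15%, 50.9% rises to 56.0% (R² 0.09) and 52.9% to 60.5% (R² 0.19). At 15% v 15%, 93.2% rises to 95.8% (R² 0.12) and 92.8% to 97.0% (R² 0.22). The Monte Carlo standard error near 50% is about 1.1 points (√(0.25/2000)).
- Over AUC 0.75 to 0.85, the gain is about 2 to 9 points with three continuous covariates. With the full SAP 11.1 set, all categorical, it is about 1 to 7 points, because the variance cut falls to about 3% to 18%. The step 3 formula agrees at 10% v 15%: a 3% cut gives 53.0% and an 18% cut gives 59.0%.
- Deaths are few: 25 + 37.5, about 62, at the phase II rates, or 50 if both arms are at 10%. This favours a short, continuous covariate set.

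**6. Is the crude limit valid?** At the margin (true 10% v 20%), under simple allocation, both the crude and the adjusted test rejected about 5% to 6% of the time against a nominal 5%. Under effective covariate-adaptive balance the crude test rejected 3.5% to 4.3% and the adjusted test 4.3% to 5.0%. Such balance is doubtful here. SAP 6.0 starts adaptive allocation at a site only after four or six patients per arm, that is 8 or 12 patients. The protocol synopsis plans 90 to 100 centers, an average of 500/100 = 5.0 to 500/90 = 5.6 per site. Unless enrolment is concentrated in a few sites, most patients would be allocated by within-site blocks.

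**The case against.** **The case for leaving SAP 14.1 alone.** A crude difference is inferred from silence; the standardized estimator of SAP 11.1 is itself a risk difference, and 14.1 does not exclude it. SAP 8.0 says the study was not powered for safety and favours caution, and a wider limit errs against declaring surgery safe. Covariate-adjusted mortality is already planned elsewhere, in the Cox models of SAP 13.2. The larger gains arise where surgery truly carries excess mortality; with equal arms at 10% there is little left to gain.

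**What stands.** All of these facts stand, and they lower the weight of the point. They do not remove it. The crude difference is the natural reading of SAP 2.3 and 14.1, and leaving the estimator of a primary decision rule open has the same remedy. The Cox models do not feed the margin. Adjustment keeps error at the margin near 5%, so the precision is not bought by a laxer test.

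**Stronger readings a reader might infer.**
- That the crude limit is too wide, in the sense of over-covering. This needs allocation that really balances the factors, which the run-in and the average site size make doubtful.
- That the trial loses 4 to 10 points of planned safety power. No safety power is planned, the AUC is an assumption, and a gain of that size needs strong prognosis together with a true excess near 5 points or higher mortality. The 40% in Protocol 2.1 describes ICH in general, not this trial's phase II population.
- That the trial is less able to show harm. Only non-inferiority power was calculated here, and the documents give nothing that settles it.

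**Conclusion.** The point holds as a free improvement. SAP 14.1 states no covariate adjustment for the 30-day mortality margin test, although the SAP adjusts the efficacy risk difference for the same allocation factors to gain precision. The crude limit is valid, slightly conservative if adaptive allocation achieves real balance, and less precise than it could be. The gain is about 1 to 9 points of non-inferiority power, depending on mortality and on how the covariates are coded: about 2 to 9 at the phase II rates, and about 1 to 5 if both arms are at 15%. This rests on an assumed AUC of 0.75 to 0.85 for 30-day death, 250 patients per arm and mortality near the phase II level. With weaker prognosis, or with both arms at 10%, the gain is at or below the bottom of the range.

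**What to change.** In SAP 14.1, specify for 30-day mortality the standardized (g-computation or TMLE) risk difference and its upper one-sided 95% limit, compared with the 10-point margin. Adjust for GCS, age and clot volume, entered as continuous terms rather than in the categorical coding of SAP 11.1, and name the interval method. Report the crude difference and its limit as supporting. Leave the rarer safety outcomes (infection, rebleeding, first-week mortality) unadjusted, and say so.

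The cost is a sentence or two of SAP wording and a simpler version of an estimator that the SAP already defines. It needs no new data, patients or visits. It should be settled before unblinding, so that the choice of limit cannot depend on the result.

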14.2. Total SAEs at 30 Days

Mortality attributed to MIS+rt-PA treatment plus disease-associated adverse events are similar to the morbidity and mortality attributed to medical management in the first 30 days. Analyses: For initial evaluations, differences between the MIS+rt-PA intervention and medical management groups will be examined using a logistic regression model.

14.3. Summary of Adverse Events and Serious Adverse Events by MedDRA Code and Grouped by Organ System

All AEs and SAEs are summarized by type and by treatment group in terms of frequency of the event, number of subjects having the event, timing relative to randomization, severity (mild, moderate, severe), and relatedness to the study treatment (definitely, probably, possibly, definitely not). At the end of the study, the cumulative incidences of these events will be compared between the two treatment groups using Fisher's exact test. Statistically significant differences between the treatment arms will be assessed after adjustments for multiplicity in the case of individual SAE/AE diagnoses and MedDRA codes. Additionally, generalized linear mixed models for binary data will be used to examine AE and SAE probabilities between treatment groups while accounting for potential confounders and site-clustering effects.

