8.0. Multiplicity

The primary analysis of efficacy is tested at the two-sided alpha level of 0.05. In addition, secondary analyses will consider the alpha=0.05 two-sided type I error. Secondary analyses will be examined in the order specified and will not be corrected for multiplicity of testing.

Secondaries 2-7 are defined. The other analyses without specific hypotheses are considered exploratory. We will present descriptive statistics and CIs.

For safety outcomes, we do not account for multiplicity as this study was not powered to observe safety. Thus, a cautionary approach is justified.

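### SAP 14.2 calls total 30-day morbidity and mortality similar between arms, but plans only a logistic regression for differences, with no margin or confidence-limit criterion

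*SAP*

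**What the plan says.** - SAP 2.3.1 lists total SAEs at 30 days as a safety measure in its own right (item e), apart from mortality, bleeding and infection. SAP 14.1 adds that total SAEs will be compared between the treatment groups.
- SAP 14.2 gives the expectation for that measure: "Mortality attributed to MIS+rt-PA treatment plus disease-associated adverse events are similar to the morbidity and mortality attributed to medical management in the first 30 days". The analysis, introduced as serving initial evaluations, is that "differences between the MIS+rt-PA intervention and medical management groups will be examined using a logistic regression model". No margin, interval criterion, significance level or covariate list is given, and no later evaluation of total SAEs with a margin follows.
- SAP 14.3 plans further AE and SAE comparisons: "the cumulative incidences of these events will be compared between the two treatment groups using" Fisher's exact test, plus mixed models. These also test for differences.
- SAP 14.1 takes a different route for the primary safety events. Its null is that MIS+rt-PA is worse, and "Methods of non-inferiority will be used to statistically determine if the proportions of a particular type of SAE" are acceptably close. For this, "the tolerance value will be defined as 10% for the primary adverse events of 30-day mortality, rebleeding, and infection", and "5% for first-week operative mortality". The criterion is that the upper one-sided 95% limit on the rate difference does not exceed the tolerance. No tolerance is set for total SAEs.
- SAP 8.0 says: "For safety outcomes, we do not account for multiplicity as this study was not powered to observe safety".

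**The concern.** The statement in 14.2 is one of similarity, while the named analysis has equality as its null. Failing to reject equality shows only that the data did not rule it out; it puts no ceiling on the excess harm that remains compatible with the data. The less information the trial has, the more easily such a result arises, and the SAP itself says the trial was not powered for safety.

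At stake is the conclusion on total SAEs. This is the listed 30-day comparison that would pick up serious harms other than death, bleeding and infection. As written, none of the analyses planned for it can support the statement attached to it, although 14.1 already contains a method that could.

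**Working it through.** **Inputs.** 250 per arm (SAP 2.1). Upper one-sided 95% limit (SAP 14.1). Assumptions: two-sided 0.05 for the 14.2 test, which states no level (0.05 is the level SAP 8.0 gives for efficacy); an unadjusted comparison in place of the logistic model; and a medical-arm rate of at least one SAE by day 30 of 20–50%, because the documents give no rate.

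**Check of the formula on the plan's own figure.** For a difference test of p0 against p1 with d = p1 − p0 and p̄ their mean:

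power = Φ((d − 1.96·SE0)/SE1), with SE0 = √(2p̄(1−p̄)/250) and SE1 = √((p0(1−p0) + p1(1−p1))/250).

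Protocol 9.1.9 gives 88% power for 25% against 38%. Here SE0 = 0.0415 and SE1 = 0.0411, so (0.13 − 0.0814)/0.0411 = 1.18 and power is 88.1%. All eight cells of the Protocol's power table (section 9.1.9, Table 2) reproduce to within about half a point.

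**Difference test for total SAEs.** Example, 30% against 40%: SE0 = √(2 × 0.35 × 0.65/250) = 0.0427 and SE1 = √((0.21 + 0.24)/250) = 0.0424. Then (0.10 − 0.0836)/0.0424 = 0.386, power is 65%, and the chance of non-significance is 35%. Chance of a non-significant result for other values:

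| Assumed control rate | 5-point excess | 8 points | 10 points | 15 points |
|---|---|---|---|---|
| 20% | 73% | 45% | 27% | 3% |
| 30% | 78% | 53% | 35% | 6% |
| 40% | 80% | 56% | 39% | 8% |
| 50% | 80% | 57% | 39% | 7% |

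With an unpooled standard error throughout, the 20% control, 10-point cell is 26% instead of 27%. So a 10-point excess is missed about 26–39% of the time across these rates. The excess detectable with 80% power is about 12 to 12.5 points for control rates of 30–50%.

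**Dependence on information.** With half the patients (125 per arm), 30% against 40% gives SE0 = 0.0603 and SE1 = 0.0600. Then (0.10 − 0.1183)/0.0600 = −0.304, and non-significance rises from 35% to 62%. The same true harm looks more like similarity in the smaller trial.

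**Upper-limit method, borrowing 10 points for illustration only.** The chance that the upper limit falls within the margin is Φ((0.10 − d)/SE1 − 1.645). At 30% in both arms, SE1 = √(2 × 0.21/250) = 0.0410 and 0.10/0.0410 − 1.645 = 0.795, which gives 79%.

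| Assumed control rate | True equality | 5-point excess | 10-point excess |
|---|---|---|---|
| 30% | 79% | 33% | 5% |
| 40% | 74% | 30% | 5% |
| 50% | 72% | 30% | 5% |

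For 80% power at true equality, 260, 297 and 310 patients per arm would be needed at these three rates.

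**The case against.** The strongest reply is that 14.2 never says a non-significant result will be read as similarity. The logistic model is offered for initial evaluations. Elsewhere, for example in 13.6 on ICU intensity, the SAP opens a section with an assertion of what is expected and then names routine models, so the 14.2 sentence may be the same template. SAP 8.0 treats analyses without specific hypotheses as exploratory, to be shown with descriptive statistics and confidence intervals. Its remark on power explains why safety tests go uncorrected for multiplicity, a choice it calls cautionary and one that makes harm easier to flag. Total SAEs is also not one of the primary safety measures named in 14.1.

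Much of this stands. It makes the defect one of an unsupported statement, not of a declared faulty rule. It does not remove the defect: 14.2 does state an expectation of similarity, so it is unclear whether the exploratory clause in 8.0 covers it, and no interval criterion is attached.

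Three stronger readings are tempting, and the documents do not support them.

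- *A reader might infer that non-significance is the only support for safety.* It is not. Section 14.1 has margin-based tests for 30-day mortality, rebleeding, infection and first-week mortality, so the mortality part of the 14.2 sentence is already covered. At 10% 30-day mortality in both arms (the Phase II medical-arm rate in Protocol 2.2), that test passes 98% of the time; at a true 10-point excess it passes 5% of the time. Recruitment-suspension thresholds and DSMB review add to this.
- *A reader might infer that non-significance is likely whatever the real harm.* At control rates of 30–50% it is more likely than not only for excesses up to about 8 points; at 15 points it is 6–8%.
- *A reader might take 10 points as the plan's tolerance for total SAEs.* It is set only for 30-day mortality, rebleeding and infection.

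**Conclusion.** The point holds for total SAEs at 30 days and no further. SAP 14.2 says outcomes "are similar to the morbidity and mortality attributed to medical management in the first 30 days", but neither its logistic model nor the tests in 14.3 can support that statement, and no margin or confidence-limit criterion is given, unlike for the primary safety events in 14.1.

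The size depends on a medical-arm SAE rate that the documents do not give. At an assumed 30%, true excesses of 5, 8 and 10 points go undetected about 78%, 53% and 35% of the time; over 20–50%, a 10-point excess is missed about 26–39% of the time. These figures also assume 250 analysed per arm, two-sided 0.05 and no covariate adjustment. The logical gap between the statement and the test does not depend on any of these assumptions.

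**What to change.** In SAP 14.2:

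1. Define the measure as patients with at least one SAE by day 30, and report the risk difference (MIS+rt-PA minus medical management) with its upper one-sided 95% limit.
2. Keep the logistic model as a descriptive adjusted analysis, and state that non-significance is not read as similarity.
3. Claim similarity only if the upper limit lies within a tolerance prespecified and justified for total SAEs. If the 10 points from 14.1 is to be borrowed, it needs its own justification.
4. If no tolerance can be justified, drop the word *similar* and present the difference and its interval descriptively.

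This takes a few sentences and no new data. The downside is that the similarity claim can fail. With a borrowed 10-point tolerance and control rates of 30–50%, an equally safe treatment would miss the criterion about 21–28% of the time (100% minus 79% and 72%), and a true 5-point excess would still pass 30–33% of the time. The descriptive option avoids the first cost by making no claim.
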